6.8. Storage and Analysis of Samples

Not applicable.

6.9. End of Study

The end of study will be defined as 'last participant last visit' i.e., the date at which the last participant has completed their final study process. The CI will notify the Sponsor, participating sites and REC within 90 days of the end of study. If the data collected in this pilot trial is considered an internal pilot rather than an external pilot we will use the data in the main trial.

7. SAFETY REPORTING

7.1. Definitions

Term	Definition
Adverse Event (AE)	Any untoward medical occurrence in a trial participant (i.e., any
	unfavourable and unintended sign, symptom or disease), which is
	related to study ulcer and/or to the study treatments (intervention or
	control).
Serious Adverse	A serious adverse event is any untoward medical occurrence that:
Event (SAE)	results in death
	is life-threatening
	requires inpatient hospitalisation or prolongation of existing
	hospitalisation

- · results in persistent or significant disability/incapacity
- consists of a congenital anomaly or birth defect

Other 'important medical events' may also be considered serious if they jeopardise the participant or require an intervention to prevent one of the above consequences.

NOTE: The term "life-threatening" in the definition of "serious" refers to an event in which the participant was at risk of death at the time of the event; it does not refer to an event which hypothetically might have caused death if it were more severe.

7.2. Operational Definitions for (S)AEs

An adverse event (AE) in this pilot trial is any untoward medical occurrence in a participant to whom a trial intervention or procedure has been delivered, including occurrences which are not necessarily caused by or related to that intervention or procedure.

Examples of AEs which may be expected would be:

- Re-ulceration
- New ulcer
- Ulcer infection

AEs which are NOT considered related to the intervention or procedure do not need to be reported unless they are considered SAEs.

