7.3. Recording and Reporting SAEs

HCPs will record all directly observed AEs and all SAEs reported by the trial participants up to the final follow-up assessment. In addition, sites should follow their own local procedures for the reporting of any adverse events linked to clinical care.

Adverse events should be entered onto the Adverse Event reporting form and reported to York Trials Unit within five days of discovery or notification of the event.

SAEs should be entered onto the Serious Adverse Event reporting form and reported to York Trials Unit within 24 hours of discovery or notification of the event. Once received, causality and expectedness of the SAE will be confirmed by the Chief Investigator or another clinical member of the Trial Management Group (if the CI is unavailable).

SAEs that are deemed to be unexpected and related to the trial will be notified to the Research Ethics Committee (REC) and Sponsor within 15 days. All such events will be reported to the Trial Steering Committee at their next meeting.

All events will be followed up until the event resolves or a decision is made for no further follow up. Participants experiencing SAEs which are deemed to be related to the trial treatments (intervention or control) and which remain ongoing at the time of participant trial exit will be followed up for one further month beyond trial exit.

Where repeated adverse events (serious or non-serious) of a similar type are observed, these will be discussed with the TMG and other relevant groups and will be onward reported to the REC and Sponsor should concerns be raised in relation to the type of event and/or frequency observed.

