7.3.1.2 Causality

Clinical judgement will be used to determine the relationship between the study procedures and the occurrence of each AE;

- Not-related: There is no evidence of a causal relationship between the event and study procedures.
- Related: There is evidence of a causal relationship between the event and study procedures, i.e., a relationship to the study procedures cannot be completely ruled out.

Assessment of causality must be made by a medically qualified doctor (usually the Principal Investigator).

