9.4. Statistical Analysis

A statistical analysis plan (SAP) giving details of the planned analyses will be drafted before data collection has been completed, and reviewed by the Trial Management Group and the Trial Steering Committee. A brief description of the planned analyses is given below.

The statistical analysis will be carried out by a statistician at York Trials Unit, using Stata v16 or later. The analysis and reporting of this pilot trial will follow CONSORT guidelines [34,35]. A flow diagram will be produced, depicting the flow of participants through the trial. The number of participants screened, eligible, consenting and randomised will be summarised, with reasons for ineligibility and non-consent given where available.

Baseline data will be summarised by randomised group, with no formal statistical comparisons being undertaken [36]. Continuous variables will be summarised using descriptive statistics (n, mean, standard deviation, median, minimum, maximum), while categorical variables will be summarised using counts and percentages. Participant outcomes will be summarised descriptively by randomised group and time point, including the amount of missing data. This study is a pilot trial, and as a result statistical hypothesis testing of outcomes will not be carried out.

For the intervention group, attendance of the one-to-one sessions and use of the web-based maintenance intervention will be summarised descriptively.

Adverse events will be summarised descriptively by treatment group.

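### Sections 7.1, 7.2 and 7.3 give adverse-event rules that cannot all be followed, and the by-arm AE summary is comparable only if it rests on the notes review that covers both arms

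*Protocol*

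**What the plan says.** Four statements in the Protocol govern what counts as an adverse event and what is passed on.

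- **7.1 Definitions** restricts AEs to events "related to study ulcer and/or to the study treatments", in either arm.
- **7.2 Operational Definitions** covers any untoward occurrence after a trial intervention or procedure, "including occurrences which are not necessarily caused by or related to that intervention or procedure". Re-ulceration, new ulcer and ulcer infection are listed as expected examples.
- **7.2, last sentence**, adds an exemption: "AEs which are NOT considered related to the intervention or procedure do not need to be reported unless they are considered SAEs".
- **Section 7.3**, on what is recorded, says "HCPs will record all directly observed AEs and all SAEs reported by the trial participants up to the final follow-up assessment". On what goes to the trials unit, it says "Adverse events should be entered onto the Adverse Event reporting form and reported to York Trials Unit within five days of discovery". Neither sentence depends on relatedness.

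Other sections bear on the use of these data. 7.3.1.2 has a medically qualified doctor judge causality. It describes a related event as one with evidence of a causal link, and then explains this as meaning that "a relationship to the study procedures cannot be completely ruled out". 6.6.1 lists AEs and SAEs among the clinical outcomes that blinded assessors extract from health records at three months, with no restriction by arm. The AE row in Appendix 1 is marked at baseline, weeks 1-8, three months and four months, without the intervention-only asterisk. Section 9.4 states: "Adverse events will be summarised descriptively by treatment group". It names neither the source nor the definition.

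**The concern.** There are two linked problems. First, the rules conflict on the events most likely to occur in this population, namely non-serious foot events that nobody attributes to REDUCE. Two sites could each comply with the protocol and send different AE counts to the trials unit.

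Second, parts of the system do not act equally on the two arms. The 7.2 exemption keeps a non-serious event only if it is linked to the intervention or a procedure, and controls receive no REDUCE. Prospective recording may also rest with staff who see intervention participants only. A table by arm built on that route would partly show how closely each arm was watched and how the filter worked.

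There is some practical weight behind this even in a pilot. 7.3 asks for repeated AEs of similar type to be discussed and, if there is concern about type or frequency, passed on, which needs consistent counts. Sections 1.3 and 6.9 also leave open that the pilot data may be used in the main trial.

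**Working it through.** The protocol states no figure to reproduce here. The check sets the rules side by side for one event, counts scheduled contacts, and then shows what pooling two recording routes could do.

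**Step 1. One test event.** Take a non-serious ulcer infection that nobody links to REDUCE or to a study procedure.

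| Rule | Result |
|---|---|
| 7.1 definition | AE, because it is ulcer-related |
| 7.2 definition | AE regardless of cause, and a listed example |
| 7.2 exemption | Need not be reported; a link to the ulcer does not count |
| 7.3 recording | Recorded if directly observed |
| 7.3 reporting | Sent to the trials unit within five days |

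The exemption can sit beside the 7.2 definition, since one concerns reporting and the other meaning. It cannot be squared with the 7.3 reporting sentence, and it sets aside the ulcer link that 7.1 treats as sufficient.

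**Step 2. The filter by arm.** A control participant undergoes study procedures such as questionnaires but no REDUCE sessions. An intervention participant has both. Under the looser wording of relatedness in 7.3.1.2, more intervention-arm events could pass the filter for the same clinical event. Few control events are likely to pass.

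**Step 3. Scheduled REDUCE contacts.** From 6.5 there are 8 sessions of about one hour per intervention participant and 0 per control. From 6.3 and 9.1, allocation is 2:1 with 15-20 participants.

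- N = 15: 10 versus 5 participants; 10 × 8 = 80 sessions versus 0.
- N = 20: about 13 versus 7 participants; 13 × 8 = 104 sessions versus 0.
- Notes review (6.6.1): one per participant in both arms, at three months.

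**Step 4. Effect of pooling (illustrative).** Let p be the true AE risk, equal in both arms; c the chance that the notes review captures an event, equal in both arms; and s the chance that a REDUCE session captures it, in the intervention arm only. The protocol gives none of these, so all are assumptions, and the two routes are taken as independent.

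- Recorded risk, intervention: p × [1 − (1 − c)(1 − s)]
- Recorded risk, control: p × c
- Ratio: [1 − (1 − c)(1 − s)] / c, in which p cancels

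| c | s = 0.5 | s = 0.9 |
|---|---|---|
| 1.0 | 1.00 | 1.00 |
| 0.8 | 0.90/0.80 = 1.125 | 0.98/0.80 = 1.225 |
| 0.5 | 0.75/0.50 = 1.50 | 0.95/0.50 = 1.90 |

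With the notes review alone in both arms the ratio is c/c = 1.00 for any equal c. If session capture were the only source (c = 0), controls would record nothing.

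**The case against.** The strongest reply is that a comparable source already exists. The blinded notes review takes AEs and SAEs from the records of both arms, and the choice of source for the 9.4 table may properly be made in the SAP, which is not available here. That stands: non-comparability is conditional on pooling the routes or using the session route alone. It does not answer the contradiction in 7.1-7.3, which is in the protocol's own text and also governs what staff send to the trials unit.

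It is also fair that SAEs are reportable whatever their cause, and that ulcer-free days, time to re-ulceration, number of ulcers, hospital days, amputations and deaths are collected separately in both arms. What is exposed is mainly non-serious AEs. Ulcer infection is the clearest case, because it has no line of its own in the 6.6.1 outcome list.

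A reader might infer several stronger things that the documents do not support.

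- *Control AEs are zero by construction.* Controls undergo study procedures, 7.1 covers the control treatment, and the threshold in 7.3.1.2 is low. Few is likely; zero is not built in.
- *Only REDUCE staff record AEs.* 7.3 does not define HCPs. Section 6.1.1.2 points to REDUCE deliverers, but 6.6.1 uses the term for assessors who do not deliver it.
- *There are ten live contacts against none.* That adds two interviews, which 6.6.4 gives to a university qualitative researcher and does not tie to AE recording. The supportable count is eight sessions against none.
- *The intervention arm has a longer AE window, four months against three.* The Appendix 1 AE row carries no intervention-only mark at four months, so as written the window is the same.
- *Blinded assessors must judge relatedness to an allocation they do not know.* 7.3.1.2 gives causality to a doctor.

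**Conclusion.** The point holds as a conflict of rules with a conditional effect on comparability. Sections 7.1, 7.2 and 7.3 cannot all be followed for a non-serious ulcer event not attributed to REDUCE, and the 7.2 exemption bears unevenly on the usual-care arm. If HCPs means REDUCE deliverers, prospective capture is also unequal, and the table in 9.4 would be non-comparable if session-observed events were pooled with the notes review or replaced it.

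The size cannot be taken from the documents. Under equal true risk, notes-review capture of 0.5-1.0 and session capture of 0.5-0.9, the recorded-risk ratio runs from 1.00 to 1.90.

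The summary is descriptive, no hypothesis is tested, and AE comparison is neither an objective (2.1) nor a stop-go criterion (9.2). The consequence is a misleading table and inconsistent safety counts, not a wrong test result. This should be fixed; it does not threaten the pilot's feasibility aims.

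**What to change.** - Reconcile 7.1-7.3 to one AE definition and one recording rule, applied identically in both arms. Record non-serious ulcer events and all SAEs regardless of relatedness.
- Give ulcer infection its own item on the notes-review form.
- Keep one wording of relatedness, judged by the doctor named in 7.3.1.2, and use it for expedited reporting only, not to decide what is recorded.
- State in 7.3 who the HCPs are.
- In 9.4, base the by-arm AE summary on the blinded notes review from randomisation to three months. List events observed in REDUCE sessions separately, as intervention-arm only.

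The cost is a short amendment to 7.1-7.3 with a sentence in 9.4, small changes to the AE and notes-review forms, and a few more non-serious events to enter. The notes review is already planned for every participant.

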7.3. Recording and Reporting SAEs

HCPs will record all directly observed AEs and all SAEs reported by the trial participants up to the final follow-up assessment. In addition, sites should follow their own local procedures for the reporting of any adverse events linked to clinical care.

Adverse events should be entered onto the Adverse Event reporting form and reported to York Trials Unit within five days of discovery or notification of the event.

SAEs should be entered onto the Serious Adverse Event reporting form and reported to York Trials Unit within 24 hours of discovery or notification of the event. Once received, causality and expectedness of the SAE will be confirmed by the Chief Investigator or another clinical member of the Trial Management Group (if the CI is unavailable).

SAEs that are deemed to be unexpected and related to the trial will be notified to the Research Ethics Committee (REC) and Sponsor within 15 days. All such events will be reported to the Trial Steering Committee at their next meeting.

All events will be followed up until the event resolves or a decision is made for no further follow up. Participants experiencing SAEs which are deemed to be related to the trial treatments (intervention or control) and which remain ongoing at the time of participant trial exit will be followed up for one further month beyond trial exit.

Where repeated adverse events (serious or non-serious) of a similar type are observed, these will be discussed with the TMG and other relevant groups and will be onward reported to the REC and Sponsor should concerns be raised in relation to the type of event and/or frequency observed.

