6.6. Data Collection

6.6.1. Clinical Team Completed Case Report Forms (CRFs)

Case report forms will be used to collect the following clinical and demographic data:

- Screening:
 - Inclusion and exclusion criteria;
- Baseline:
 - o Participant contact details name, address, telephone number and email address
 - Demographics (date of birth) and NHS number;
 - Previous medical history duration (years) and type of diabetes, most recent HbA1c value if available, depression, documented peripheral neuropathy, documented peripheral arterial disease (PAD), visual impairment, other relevant conditions;
 - Diabetic foot ulcer (DFU) history single ulcer versus multiple ulcers, most recent episode confirmed healing date, activity/education/footwear;
- Clinical outcomes (via notes review by blinded outcome assessors)
 - Ulcer-free days;
 - Days to re-ulceration (if re-ulceration occurs);
 - Number of ulcers;
 - Days in hospital;
 - AEs;
 - SAEs;
 - Amputations major and minor;
 - Mortality;

Resource use data.

The clinician baseline CRF will be completed on paper, a copy will of the completed CRF will be securely stored in the site ISF and the original CRF will be posted to YTU.

Healthcare professionals who are not involved in delivering the REDUCE intervention, the research outcome assessors (nurses or practitioners), will support the collection of Clinical Outcome data at three months post randomisation. Data will be collected from relevant health care records, to include but not limited to, secondary care, GP, community health and community podiatry records. Paper forms will be provided, a copy will of the completed CRF will be securely stored in the site ISF and the original CRF will be posted to YTU.

Intervention session details will be collected and will include:

- Session number;
- Date:
- Attendance:
- Session delivered by;
- Length of session;
- Interventions/modalities delivered;
- Completion of home practice.

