6.6.2. Participant completed CRFs

All participants will be asked to complete demographic and general information about their health following consent including: sex, declared ethnicity, marital status, smoking status, COVID-19 exposure, income, highest level of education, and employment status.

To assess the psychological and behavioural outcomes, they will be asked to complete the following validated questionnaires at baseline (prior to randomisation), and at six weeks and three months post randomisation:

- Brief Illness Perception Questionnaire (B-IPQ):
 Examines the participant's perception of their illness [22].
- Cognitive and Behavioural Responses Questionnaire (CBRQ) short version; sub-set of items:
 - Examines participant's beliefs about their symptoms [23].
- Generalised Anxiety Questionnaire (GAD-7): Assesses anxiety [24].
- Patient Health Questionnaire-9 (PHQ-9): Assesses depression [25].
- International Physical Activity Questionnaire Elderly (IPAQ-E) short form: Assesses participant physical activity [26].
- Mental Health Continuum Short Form (MHC-SF):
 Examines emotional, psychological and social well-being [27].
- Nottingham Assessment of Functional Footcare (NAFF):
- Scale of Positive And Negative Experience (SPANE-P) positive items only: Examines positive feelings [29].
- Social Provisions Scale (SPS): Examines social relationships and support [30].

Examines foot self-care behaviours [28].

For the health economic analysis, participants in both arms will be asked to complete the following questionnaires at baseline and three months only:

- ICEpop CAPability measure for Adults (ICECAP-A):
 Measures capability in adults including attachment, stability, achievement, enjoyment and autonomy [31].
- EQ5D-5L consisting of the EQ5D descriptive system and the EQ Visual Analogue Scale (EQ VAS):
 - Measures mobility, self-care, usual activities, pain/discomfort and anxiety/depression [32].
- Items on resource use

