6.6.4. Interviews with Participants in Intervention Arm

All participants in the intervention arm will be invited to be interviewed at baseline and approximately four months in order to examine: their understandings and expectations of the intervention and recruitment experiences; their likes/dislikes of the initiation and maintenance components of REDUCE; reasons for engagement and non-engagement with these components; and their views about how REDUCE might be further refined to optimize uptake and engagement. These interviews will be undertaken by an experienced qualitative researcher at the University of Edinburgh, by telephone or virtually at a time convenient to participants. They are expected to last

around 45-60 minutes (although this will depend on what participants have to say) and will be digitally audio recorded using an encrypted device and transcribed.

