14. APPENDICES

14.1. Appendix 1 – Schedule of Assessments: Participants

	Visits													
Procedures	Screening	Baseline	Treatment Phase Post randomisation									Follow up Post randomisation		
			Week 1	Week 2	Week 3	Week 4	Week 5	Week 6	Week 7	Week 8	6 weeks	3 months	4 months	
Inclusion/Exclusion criteria	Х	Х												
Discuss study with patient	Х	Х												
Informed consent		Х												
Demographics/ Contact information		Х												
Web-based randomisation		Х												
Brief IPQ		Х									Х	Х		
CBRQ-SF		Х									Х	Х		
SPANE-P		Х									Х			
GAD-7		Х									Х	Х		
PHQ-9		Х									Х	Х		
IPAQ-SF		Х									Х	Х		
MHC-SF		Х									Х	Х		
NAFF		Х									Х	Х		
SPS		Х									Х	Х		
ICECAP-A		Х										Х		
EQ5D-5L & EQ VAS		Х										Х		

	Visits												
Procedures	Screening	Baseline	Treatment Phase Post randomisation									Follow up Post randomisation	
			Week 1	Week 2	Week 3	Week 4	Week 5	Week 6	Week 7	Week 8	3 months	4 months	
Resource use questionnaire		Х									Х		
Telephone/virtual interview*		Х										Х	
REDUCE intervention 1:1 sessions*			Х	Х	Х	Х	Х	Х	Х	Х			
Complete home practice*			Х	Х	Х	Х	Х	Х	Х				
Homework Rating Scale				Х						Х			
Website access data*												Х	
Clinical data collection											Х		
Audit and monitoring	Х	Х	Х	Х	Х	Х	Х	Х	Х	Х	Х	Х	
Adverse events and SAs		Х	Х	Х	Х	Х	Х	Х	Х	Х	Х	Х	
Approximate Time Estimate (mins)	30	90	90	100	90	90	90	90	90	75	120	75	

^{*} Intervention arm only

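### The end of adverse-event recording is undefined and only the intervention arm has a scheduled contact at four months, so the by-arm harm summary can compare unequal windows

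*Protocol*

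**What the plan says.** - **Recording period.** Section 7.3: "HCPs will record all directly observed AEs and all SAEs reported by the trial participants up to the final follow-up assessment". No month is given, no arm is named, and the closing assessment is not defined anywhere else.
- **Assessments in both arms.** Section 6.6.2 schedules the psychological and behavioural questionnaires "at baseline (prior to randomisation), and at six weeks and three months post randomisation". Section 6.6.1 has outcome assessors who "will support the collection of Clinical Outcome data at three months post randomisation". AEs and SAEs are on the list of outcomes they take from the notes, with no distinction by arm.
- **Assessments in one arm.** Section 6.6.4: "All participants in the intervention arm will be invited to be interviewed at baseline and approximately four months". In Appendix 1 the row "Telephone/virtual interview" and the website-data row are the participant procedures ticked at four months. Both carry the asterisk that means "Intervention arm only".
- **Adverse-event row.** In Appendix 1 the row "Adverse events and SAs" is ticked at baseline, weeks 1 to 8, three months and four months, without the asterisk.
- **Analysis.** Section 9.4: "Adverse events will be summarised descriptively by treatment group". No window or person-time is named.
- **Overall duration.** The study summary gives four months of follow-up, and section 6.6.2 says participation lasts up to four months. Neither splits this by arm.

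**The concern.** A by-arm count of adverse events is interpretable only if both arms are observed for the same length of time, or if the counts are related to time at risk. Here the recording period ends at an event in the schedule and not at a fixed time from randomisation, and the schedules of the two arms differ after three months. Applied participant by participant, section 7.3 can run to about four months for someone with an interview and stop at three months for someone without one. With equal true event rates, the intervention arm would then tend to show more events per person.

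The pilot will not decide anything on harm by a test. However, section 1.3 says that it mirrors the main features of the later trial, and sections 1.3 and 6.9 leave open counting its data in that trial. An unreconciled window could therefore be carried forward.

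**Working it through.** The protocol states no adverse-event rate and no figure that bears on this point, so there is nothing to reproduce. The check sets the schedules side by side and then bounds the effect.

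**1. Scheduled routes by which an event could come to notice**

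| Time from randomisation | Intervention arm | Control arm |
|---|---|---|
| Treatment phase | Eight weekly sessions where possible, over at most 12 weeks (6.5) | No sessions (6.5) |
| Six weeks | Questionnaire (6.6.2) | Questionnaire (6.6.2) |
| Three months | Questionnaire; blinded notes review including AEs and SAEs (6.6.1, 6.6.2) | The same |
| Four months | Interview; website data (6.6.4, Appendix 1) | None, although Appendix 1 ticks the adverse-event row |

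The four-month tick thus has no control-arm contact behind it. The missing asterisk is also weak evidence of what was intended. The Homework Rating Scale row has none either, yet section 6.6.2 gives that questionnaire to the intervention arm only.

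**2. Exposure per person**

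Let *f* be the fraction of month four effectively captured in the intervention arm, with none captured in controls. The exposure ratio is (3 + *f*)/3. At a constant rate, the share of intervention-arm events falling outside the shorter window is *f*/(3 + *f*).

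| *f* | Ratio | Share outside |
|---|---|---|
| 0 | 3/3 = 1.00 | 0% |
| 0.5 | 3.5/3 = 1.17 | 0.5/3.5 = 14% |
| 1 | 4/3 = 1.33 | 1/4 = 25% |

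**3. Person-months at the upper bound (*f* = 1)**

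Inputs are 15-20 participants (9.1) and 2:1 allocation (6.3).

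- N = 20: 13.33 × 4 = 53.3 against 6.67 × 3 = 20.
- N = 15: 10 × 4 = 40 against 5 × 3 = 15.
- In both cases the intervention arm holds 72.7% of exposure with 66.7% of participants.

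**4. Effect on the table with no true difference, at the upper bound**

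The event rate *r* per person-month is assumed, constant and equal in both arms. The proportion with at least one event is 1 − exp(−*rt*), with *t* = 4 or 3 months. The extra intervention-arm events at N = 20 are 13.33 × *r* × 1.

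| Assumed *r* | Intervention, 4 months | Control, 3 months | Extra events |
|---|---|---|---|
| 0.02 | 7.7% | 5.8% | 0.3 |
| 0.05 | 18.1% | 13.9% | 0.7 |
| 0.10 | 33.0% | 25.9% | 1.3 |
| 0.20 | 55.1% | 45.1% | 2.7 |

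**5. After a common three-month cut-off**

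Person-months become 40 against 20 at N = 20, and 30 against 15 at N = 15. The exposure ratio per participant is 1.00.

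**The case against.** A reader might infer that the protocol fixes a four-month window for the intervention arm and a three-month window for controls, so that the harm table is bound to count against REDUCE by a factor of 1.33. The documents do not support that, for these reasons:

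- No passage closes recording at three months for controls. The unsplit four-month duration and the adverse-event row without an asterisk point, if anything, to four months in both arms.
- The four-month contact is a qualitative interview about expectations, experience and engagement, run by a university researcher. Section 7.3 gives recording to the healthcare professionals, whose sessions may be largely over by then. Nothing says that the interview asks about adverse events.
- An equal window already exists in the three-month notes review. A summary built on that source alone would be balanced.
- Unscheduled capture is possible in both arms through usual care, participant-reported SAEs and local reporting.
- The analysis window is normal content for a statistical analysis plan, which is not available here. Its absence from section 9.4 is not a fault in itself.
- A common four-month cut-off would equalise nominal time just as well.

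The first four points stand against the stronger reading and make 1.33 a ceiling. They do not remove the ambiguity. Section 7.3 and Appendix 1 are protocol text that sites follow, and an analysis plan can filter onset dates but cannot tell sites when to stop recording or supply month-four data for controls. For the same reason, a four-month cut-off would equalise ascertainment only if a control-arm route were added. Three months needs no addition.

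**Conclusion.** The point holds as an unresolved inconsistency with a possible bias, not as a stated unequal rule. The end of recording is undefined, the schedule ticks adverse events at four months for everyone, and only the intervention arm has a scheduled contact then. The by-arm summary can therefore rest on unequal windows, and the likely direction is more events in the intervention arm.

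Exposure per person would be at most 1.33 times longer in that arm, and 1.17 times if half of month four were captured. Over the assumed rates of 0.02 to 0.20 per person-month, the upper bound is about 0.3 to 2.7 extra events at N = 20. These figures assume a constant rate and no month-four capture in controls, and the rates are not from the protocol. In a descriptive, untested table of 15-20 people the practical effect is modest. It is worth correcting because the correction is nearly free and the design may be carried into the main trial.

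**What to change.** 1. Reconcile sections 6.6.1 and 7.3 with Appendix 1 by stating one fixed end point for adverse-event recording, measured from randomisation and the same in both arms. If that end point lies beyond three months, say how control-arm events after three months are to be found. Align the four-month tick with it.
2. In section 9.4 or the statistical analysis plan, base the by-arm AE and SAE summary on events with onset from randomisation to three months, the last time point assessed in both arms.
3. List events with later onset separately and not as a comparison. Leave SAE reporting unchanged.

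**Cost.** Wording changes and an onset-date filter, with no added visits or staff if the three-month assessments remain the last shared ones. Month-four events leave the comparative table and appear only in the listing. The cut-off equalises the length of the window but not the closer observation that weekly sessions give the intervention arm, and the report should say so.
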